6.2.2 Patient number and identification

Patients will be assigned unique study numbers that will be used on all study documentation during the course of the trial. For patients who are withdrawn by an Investigator (or designee) or who voluntarily withdraw prematurely from the study, replacement patients will be enrolled only if deemed necessary by the Sponsor. Numbers will not be reused. Details on patient number assignments will be available in the study procedural manual.

6.2.3 Randomization

Not applicable.

6.2.4 Dose preparation and administration

Qualified pharmacy or clinical staff will prepare each unit dose of study drug for IV infusion. Dose preparation shall proceed as detailed in the Pharmacy Manual for this study. Briefly, an appropriate number of 10 mL drug product vials (each containing 180 mg of BIVV009) or 25 mL drug product vials (each containing 1.1 grams of BIVV009) will be pooled and diluted with saline solution to a total volume of 500 mL to administer either a 6.5 gram dose (for patients <75 kg) or a 7.5 gram dose (for patients ≥75 kg), depending on the patient's baseline (Day 0) body weight. Details are provided in the Pharmacy Manual.

BIVV009 will be infused IV by a suitable infusion pump over a period of approximately 60 minutes. (Patients with underlying cardiopulmonary disease may receive a 2-hour infusion with Sponsor approval.) The infusion catheter and tubing will be flushed both immediately before and immediately following completion of the infusion with a sufficient quantity of sterile saline for injection. For each dose, the patient's actual dose and time of dosing and if the administration is being performed at the patient's home ([Section 10.10](#), Appendix J) will be recorded in the source documents and transcribed onto the eCRFs. The administration location, rate, start time, stop time, any infusion interruptions, and total volume of investigational product actually administered will be recorded in the eCRFs. If an AE occurs during the administration of study drug, the infusion may be slowed or stopped at the discretion of the Investigator or the professional healthcare caregiver in case of home infusions (see [Section 10.10](#), Appendix J).

Patients must be monitored for acute allergic reactions during infusion and for at least 2 hours after the completion of the first administration of study drug or 1 hour after the completion of each administration of study drug thereafter. Additionally, patients undergoing home infusions will be monitored by the professional healthcare caregiver for 2 hours after the completion of the first home infusion or 1 hour after the completion of each subsequent home infusion (see [Section 10.10](#), Appendix J). Like with office visits, medications such as epinephrine and diphenhydramine, and additional emergency equipment will be available in

case an allergic reaction or anaphylaxis occurs during home infusion. Site personnel, or professional healthcare caregiver in case of home infusions (see [Section 10.10](#), Appendix J), must be qualified to detect and treat allergic reactions and anaphylaxis. See [Section 6.3.8](#) for further details regarding additional testing.

Patients should be instructed to report the development of rash, hives, pruritus, flushing, urticaria, etc, that may represent an allergic reaction to study drug. If any signs or symptoms of an allergic or anaphylactic reaction are observed during the infusion, administration of study drug must be immediately discontinued, and the patient treated as appropriate, and in case of home infusion, the investigator should be notified immediately (see [Section 10.10](#), Appendix J).

6.2.5 Blinding

Not applicable; this is an open-label study.

6.2.6 Concomitant medications

Patients will refrain from participation in any other investigational study drug trial in which receipt of any investigational drug occurred within 5 half-lives or 30 days, whichever is longer, prior to Day 0 and during the entire study.

Treatment with rituximab monotherapy or rituximab combination therapies (eg, with bendamustine, fludarabine, ibrutinib, or cytotoxic drugs) is prohibited.

During Part A, patients will not take any prescription or over-the-counter medications/products until completion of the follow-up assessments, unless prescribed by the Investigator or another physician for the treatment of an AE.

As noted in [Section 5.2](#), concurrent administration of erythropoietin and/or a daily dose of corticosteroids (equivalent to ≤ 10 mg/day of prednisone) is acceptable provided the patient has been on a stable dose during the previous 3 months; concurrent use of vitamin B12, folate and iron supplementation is acceptable provided the patient has been on a stable dose during the previous 4 weeks.

Topical therapies without risk of systemic absorption may be allowed, and non-prescription medications for treatment of minor intercurrent illnesses (headache, viral upper respiratory tract infections, etc.) are permitted at the discretion of the PI. Hormonal contraception in female patients is allowed provided patients are receiving stable treatment ≥ 3 months prior to Screening. Any medication taken by the patient during the study, along with its strength, frequency of dosing, and reason for its use, will be documented in the patient's source data and the eCRF.

6.2.7 Contraception

Women of non-childbearing potential are defined as permanently sterile (ie, due to hysterectomy, bilateral salpingectomy, bilateral oophorectomy) or postmenopausal (defined as at least 12 months post-cessation of menses without an alternative medical cause). Women who are of non-childbearing potential will not be required to use contraception.

Female patients of childbearing potential must be established on (≥ 3 months prior to Screening) and agree to continue to use the same highly effective methods of birth control (ie, contraceptive measure with a failure rate of $< 1\%$ per year) in conjunction with male barrier contraception (ie, male condom with spermicide) throughout the study and for 9 weeks after the administration of the last dose of study drug. Highly effective methods of contraception include:

- Intrauterine device (IUD; Mirena[®])
- Established use of oral, implanted, transdermal, or hormonal method of contraception associated with inhibition of ovulation
- Bilateral tubal ligation
- Permanent birth control via the Essure procedure

Male patients will be surgically sterile for at least 90 days or when sexually active with female partners of childbearing potential will be required to use a male condom with spermicide (if locally approved for use) throughout the study and for 9 weeks after the last dose of study drug.

Patients who practice true abstinence because of the patient's lifestyle choice (ie, the patient should not become abstinent just for the purpose of study participation) are exempt from contraceptive requirements. Periodic abstinence (eg, calendar, ovulation, symptothermal, postovulation methods) and withdrawal are not acceptable methods of contraception. If a patient who is abstinent at the time of signing the ICF becomes sexually active, they must agree to use contraception as described above.

For male patients, sexual intercourse with female partners who are pregnant or breastfeeding should be avoided unless condoms are used from the time of administration of the first dose until 9 weeks after administration of the last dose of study drug. Male patients are required to refrain from donation of sperm from Day 0 until 9 weeks after administration of the last dose of study drug.

6.3 STUDY ASSESSMENTS

Please refer to [Table 3](#) in [Section 6.1](#) for an overview of the study procedures and schedule of events. Data will be collected via an eCRF for each enrolled patient. All patients will provide written informed consent before any study-specific assessment is performed. A study-specific assessment is defined as a procedure that is not part of the routine assessments performed for diagnostic purposes or standard care. Screening assessments should occur within 6 weeks prior to administration of the study treatment (ie, on Days -42 to -1). The immunization status should be confirmed at least 14 days prior to the planned administration of study drug (ie, on or before Day -14).

6.3.1 Demographic data

The date of birth, sex, race, and ethnicity will be documented, as permitted by local regulations.

6.3.2 Medical history

A detailed general medical history of clinically significant diseases and surgeries will be collected during screening. Additionally, a detailed medical history of the patient's primary CAgD as well as history of all blood transfusions will be reviewed and recorded.

6.3.3 Height, body weight, and vital signs

Height, body weight, and vital signs will be documented. Vital sign measurements (including oral temperature, respiratory rate, supine blood pressure, and pulse rate) will be obtained at the time points specified in [Table 3](#). Vital signs will be measured after the patient has been supine for at least 5 minutes.

6.3.4 Electrocardiograms

A 12-lead ECG will be obtained at the time points specified in [Table 3](#). Patients will be supine for at least 5 minutes prior to obtaining an ECG measurement. The ECG should be performed before any other procedures that may affect heart rate (eg, blood draws).

The Investigator's overall interpretation of the ECG will be recorded and any abnormalities reported.

6.3.5 Physical examinations

Full and brief physical examinations will be performed at the time points specified in [Table 3](#). The time and date of the physical examinations will be recorded in the source document and eCRF, and any clinically significant changes from baseline will be recorded as AEs.

Full physical examinations will consist of the following: general appearance, head and neck, eyes and ears, nose and throat, chest, lungs, heart, abdomen, extremities and joints, lymph nodes, skin, and neurology.

Brief physical examinations will consist of the following: general appearance, chest, lungs, heart, abdomen, and skin.

6.3.6 Immunization review

The patient's medical and vaccination history will be reviewed to ensure that each patient is up-to-date with all required immunizations; if not already vaccinated against *Neisseria meningitidis*, including serogroup B *meningococcus* where available, *Haemophilus influenzae*, and/or *Streptococcus pneumoniae* within 5 years of enrollment, these will be administered following informed consent, as applicable, per [Table 3](#) and [Section 6.1.1.1](#) (screening procedures) or [Section 10.9](#), Appendix I for Japan.

6.3.7 Clinical laboratory evaluations

Clinical laboratory evaluations (including hematology panel, clinical chemistry panel, iron panel, erythropoietin, coagulation safety panel, SLE panel, virology/serology panel, disease related biomarkers and urinalysis) as outlined in [Section 10.1](#), Appendix A will be performed at the time points specified in [Table 3](#). Clinical laboratory results will be reviewed by the Investigator and results outside of the reference ranges will be documented and clinical significance noted.

Local laboratory values may be utilized for eligibility evaluation and medical management of the patient, including assessing the Hgb criteria necessitating blood transfusions. For efficacy evaluations, results from the central laboratory (when collected and available) will be recorded in the eCRF and utilized for analyses. Detailed information on the allocation of samples for central or local laboratory processing will be available in the Laboratory Manual.

6.3.8 Additional testing in case of hypersensitivity/allergic reaction

If a patient exhibits signs of a hypersensitivity/allergic reaction during study drug administration, the study drug infusion should be stopped immediately, and medical treatment provided, as appropriate.

If a suspected anaphylactic reaction occurs ([Simons 2010](#)), the following labs may be obtained per the discretion of the Investigator, after discussion with the Sponsor Medical Monitor:

- Approximately 30 to 120 minutes after the start of symptoms: blood draw for ADAs (including isotyping), tryptase, IL-6, IL-33, plasma histamine, CICs, and complement levels (CH50). A follow-up tryptase level should be obtained 8 days following the reaction.
- 24-hour urine collection for methylhistamine analysis (ideally collection should be started within 6 hours of onset of symptoms and collected even if the patient is sent to the emergency room; patient can be provided with a container for the collection).

6.4 PHARMACOKINETIC PROCEDURES

6.4.1 Pharmacokinetic and ADA blood sample collection and processing

Blood samples for PK analysis of BIVV009 levels and ADAs against BIVV009 will be collected via an indwelling catheter and/or via direct venipuncture from the arm opposite from the site of infusion. Blood samples will be collected at the time points specified in [Table 3](#). If an indwelling catheter is used, saline flushes will be used.

6.4.2 Analytical methodology (PK and ADA)

Plasma concentrations of BIVV009 and ADA titer will be determined using a validated analytical procedure. Specifics of the analytical methods will be provided in a separate document.

6.5 PHARMACODYNAMIC PROCEDURES

6.5.1 Pharmacodynamic blood sample collection and processing

Blood samples for PD analysis of the Complement System Classical Pathway levels (Wieslab assay) will be obtained via an indwelling catheter and/or via direct venipuncture. Blood samples for analysis will be collected at the time points specified in [Table 3](#). Complement assays will also be performed on samples, including:

- Total complement (CH50)

- Total C4
- C1q
- C1s

If an indwelling catheter is used, saline flushes will be used.

6.5.2 Analytical methodology (PD)

PD parameters will be determined using a validated analytical procedure. Specifics of the analytical methods and appropriate matrices for the different parameters will be provided in a separate document.

6.6 SAFETY PROCEDURES

Safety evaluations as needed for medical management of the patient may be repeated at the Investigator's (or designee's) discretion.

Every effort will be made to schedule and perform the procedures in accordance with the nominal time, giving considerations to appropriate posture conditions, practical restrictions, and the other procedures to be performed at the same time point.

The order of priority for scheduling procedures around a time point is (in descending order of priority):

- PK and PD blood sampling
- ADAs against BIVV009
- Vital sign measurements
- ECGs
- Blood and urine samples for clinical laboratory testing
- Physical examinations

6.7 ADVERSE EVENTS AND LABORATORY ABNORMALITIES

It is the responsibility of the Investigator to report all AEs in the eCRF. The AE and SAE reporting period will begin from the time the patient signs the ICF and continue through 9 weeks after administration of the last dose of study drug. Any SAE must be reported within 24 hours of the knowledge of the occurrence to the Study Medical Monitor and the designated Clinical Research Organization's (CRO) Clinical Safety Group. Refer [Section 6.7.4](#) for further details regarding SAE reporting procedures.

For urgent medical issues in which the study's Medical Director should be contacted, please refer to the study reference manual's Official Study Contact List for complete contact information.

6.7.1 Definition of adverse events

An AE is defined in the International Council for Harmonisation (ICH) Guideline for Good Clinical Practice (GCP) as “any untoward medical occurrence in a patient or clinical investigation subject administered a pharmaceutical product and which does not necessarily have a causal relationship with this treatment” (ICH E6: Section 1.2). An AE can therefore be any unfavorable and unintended sign (including an abnormal laboratory finding, for example), symptom, or disease temporally associated with the use of a medicinal (investigational) product, whether or not considered related to the medicinal (investigational) product.

6.7.1.1 Definition of adverse drug reactions

Adverse drug reactions are defined as all noxious and unintended responses to a medicinal product related to any dose administered. The phrase “responses to a medicinal product” means that a causal relationship between a medicinal product and an AE is at least a reasonable possibility (ie, the relationship cannot be ruled out).

The following categories for determining the causal relationship to the investigational medicinal product are to be used:

Probable (must have first three):

- It follows a reasonable temporal sequence from administration of study drug.
- It cannot be reasonably explained by the known characteristics of the patient’s clinical state, environmental or toxic factors, or other modes of therapy administered to the patient.
- It disappears or decreases on cessation or reduction in dose.
- It follows a known pattern of response to the suspected drug.
- It reappears upon re-challenge.

Possible (must have first two):

- It does not follow a reasonable temporal sequence from administration of the drug.
- It may readily have been produced by the patient’s clinical state, environmental or toxic factors, or other modes of therapy administered to the patient.
- It does not reappear or worsen when the drug is re-administered.

Unrelated:

An AE will be considered “Unrelated” to the use of the investigational drug if there is not a reasonable possibility that the event has been caused by the product under investigation and does not meet the criteria for drug relationship listed under possible or probable. Factors pointing toward this assessment include, but are not limited to, the lack of reasonable temporal relationship between administration of the drug and the event, the presence of a biologically implausible relationship between the product and the AE (eg, the event occurred before administration of drug), or the presence of a more likely alternative explanation for the AE.

In case of missing causality assessment in the eCRF or SAE reporting form, the event will be regarded as possibly related unless further specified. Any SAE recorded as probably or possibly related will be categorized as “related” for regulatory reporting purposes.

A serious drug reaction is an adverse drug reaction that meets the definition of a serious event (provided below).

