2.2.4 Potential risks and benefits

As previously noted, clinical proof of concept for BIVV009 was achieved in a Phase 1b study, which demonstrated immediate cessation of hemolysis and rapid correction of anemia during short-term treatment of patients with CAgD.

The human safety risk from off-target effects of mAb therapeutics is generally considered to be low, and in this regard BIVV009 is no exception. The human safety risk from short-term inhibition of the complement system also appears to be low, based upon the experience with five approved products in this therapeutic class. Long-term, complement inhibition may increase the risk of infection with encapsulated bacteria, as reflected in the product label for eculizumab (Soliris), an inhibitor of the terminal portion of the complement system. However, to provide optimal protection against infections with encapsulated bacteria, the design of this study includes an appropriate program of prophylactic vaccinations.

The risks associated with long-term inhibition of the proximal portion of the CP are presently unknown. Theoretically, it could increase the risk of SLE or circulating immune complexes (CIC) disease due to the role of the C1 complex in immune complex clearance, as observed in patients with congenital deficiencies of C1 complex components (C1q, C1s, and C1r). However, pharmacologic inhibition of C1s differs from congenital deficiency of the C1 complex because: 1) congenital C1 complex component deficiency are commonly not single gene mutations but typically are associated with second mutations in other immune system genes; 2) pharmacologic inhibition of C1s enzymatic function in the C1 complex leaves intact the non-enzymatic function of C1q, which is important for the opsonization and phagocytic removal of apoptotic cells which protects against autoimmunity; and 3) the phenotype associated with life-long, often total absence of C1 complex structure and function is unlikely to be reproduced by pharmacologic antagonism of C1 enzymatic function in fully developed adults. Nevertheless, standard clinical biomarkers related to SLE (eg, antibodies to double-stranded DNA [dsDNA]) have been incorporated into the study design as safety surveillance measures.

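### Protocol 6.7.1.1 makes unreasonable timing a condition for a Possible drug relationship, so some plausible reactions fit no category and some implausible ones count as Related

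*Protocol*

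**What the plan says.** Protocol 6.7.1.1 opens by defining an adverse drug reaction: "a causal relationship between a medicinal product and an AE is at least a reasonable possibility". It then prescribes three categories for investigators.

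- **Probable** has three mandatory criteria: reasonable timing, no reasonable alternative explanation, and positive dechallenge ("It disappears or decreases on cessation or reduction in dose").
- **Possible** has two mandatory criteria. The first is "It does not follow a reasonable temporal sequence from administration of the drug". The second is that another cause may readily have produced the event.
- **Unrelated** needs two things together: no reasonable possibility of causation, and that the event "does not meet the criteria for drug relationship listed under possible or probable". Factors listed as pointing to Unrelated include "the lack of reasonable temporal relationship between administration of the drug and the event" and "the presence of a more likely alternative explanation for the AE". The section's example of biological implausibility is that "the event occurred before administration of drug".

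A blank assessment is treated as possibly related. Serious events recorded as Possible or Probable are related for regulatory reporting. Section 8.1.2.3 of each SAP pools Possible and Probable as Related in the summary tables and counts a blank as Related. Neither SAP redefines the categories.

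**The concern.** The two conditions required for Possible are close to two of the factors offered for Unrelated, yet Possible counts as Related. A reaction of uncertain but plausible cause would normally be well timed with some competing explanation, and that is what the Possible criteria shut out.

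The relatedness call has several uses: the tabulations planned in Protocol 7.8.2, SUSAR determination (6.7.1.1 and 6.7.1.3), reporting of serious events after the follow-up period (6.7.4), the investigator's judgment on removal (6.7.2), and the condition for returning to home infusion (5.3). Long-term safety is the primary objective of Part B, and Protocol 2.2.4 says: "The risks associated with long-term inhibition of the proximal portion of the CP are presently unknown".

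**Working it through.** The plan gives no figure to reproduce; this is a check of category logic.

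**Limb 1, the gap.** Take a reasonably timed event for which causation is a reasonable possibility, but which has an alternative explanation, or a dechallenge that is negative or cannot be assessed.

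1. Probable fails, because all three criteria are mandatory.
2. Possible fails, because the timing is reasonable.
3. Unrelated fails, because causation is a reasonable possibility.

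This need not be rare. Protocol 6.7.2 allows no action on study drug, and then there is no cessation or reduction from which to judge dechallenge. A reasonably timed event with no reasonable possibility of causation is not caught; it is validly Unrelated.

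**Limb 2, the wrong inclusion.** Take a badly timed event with a ready alternative cause and no reasonable possibility of causation. It meets both Possible criteria. Unrelated excludes anything that meets Possible, so it must be called Possible. An event before the first dose with a ready alternative cause is caught in the same way. Such events are collected, because recording starts at consent (Protocol Table 3, footnote k).

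**Completeness check.** Cross timing (2 levels: reasonable or not), alternative cause (3: none, some, ready) and dechallenge (3: positive, negative, not assessable): 2 × 3 × 3 = 18 profiles. Each is taken with causation a reasonable possibility (18) and not (17, assuming that an event meeting all Probable criteria is always a reasonable possibility).

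| Rule | Reasonable possibility (18): Probable / Possible / no category | No category among the 9 reasonably timed | No reasonable possibility (17): Unrelated / Possible |
|---|---|---|---|
| As written | 1 / 3 / 14 | 8 | 14 / 3 |
| Timing criterion reversed, both still mandatory | 1 / 3 / 14 | 5 | 14 / 3 |
| Reasonable-possibility test decides | 1 / 17 / 0 | 0 | 17 / 0 |

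These count logical profiles, not events. The zeros in the last row follow by construction. A coarser grid with two levels per feature also shows both faults: 3 of 4 reasonably timed reasonable-possibility combinations fit no category, and every badly timed combination with a ready alternative is Possible.

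**Outputs touched.** The SAPs list 12 adverse event outputs for Part A and 11 for Part B, 23 in all.

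- Wholly on relatedness: the by-relationship and related-serious tables, 2 + 2 = 4.
- In part: the two overall summaries, with 2 of 9 items in Part A and 2 of 14 in Part B (10 subject counts plus 4 event counts).
- Not on relatedness: 23 − 4 − 2 = 17.

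**Sensitivity.** With 20 patients, one patient whose status changes moves a related row by 1/20 = 5.0 percentage points. The number of such patients is unknown; assuming 1 to 4, the row moves by 5 to 20 points. Part B patients are a subset of Part A (Part B SAP 3.1.1), so with fewer than 20 the step is larger.

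**The case against.** The best defence is that the section's general definition is sound and investigators will use judgment. The rules on removal, on return to home infusion and on late serious events all refer to the investigator's view. SUSAR status can be reached through the adverse reaction definition. An investigator who finds no fitting category may leave causality blank, and the blank then counts as related, which is conservative. Pre-dose events stay out of the treatment-emergent tables (Part A SAP 8.1). The profile counts depend on the grid, and reversing the timing criterion alone does help reasonably timed events (8 unclassified falls to 5).

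Much of this limits the consequences. It does not remove the contradiction. The protocol prescribes these categories, so judgment has to work against the text. Protocol 6.7.2 requires a relatedness assessment, so a blank is not an intended answer, and the default gives no criteria to someone who must choose. A sound general definition beside unsound criteria is itself the conflict. What stands is that the profile counts say nothing about frequency, that the pre-dose example shows the wording fault without touching the tables, and that no failure in practice has been shown.

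**Conclusion.** The point holds, and the text should be fixed. Protocol 6.7.1.1 contradicts itself, and both limbs follow from its wording.

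The number of events affected and the net direction of bias cannot be derived. There are no event counts, investigators' practice is unknown, and the CRF Completion Guidelines (mentioned in Protocol 7.11) are not among the documents. The reach is 4 of 23 adverse event outputs wholly and 2 in part, with a step of 5 percentage points per patient at 20 patients. Recording of all adverse events, 24-hour reporting of all serious events in the reporting period, the other 17 outputs and every efficacy analysis are unaffected.

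**What to change.** In Protocol 6.7.1.1:

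1. State the first Possible criterion positively, matching the first Probable criterion.
2. Drop the rule that the first two Possible criteria are mandatory. Define Possible as an event that misses Probable but for which a causal relationship is a reasonable possibility, including when another explanation is also plausible or dechallenge is negative or not assessable. The bullets become supporting factors. Without this step the gap only moves.
3. Keep Unrelated for events with no reasonable possibility of causation. Poor timing and a more likely alternative explanation stay as factors that do not decide alone, since timing may be hard to judge while the long-term risks are unknown.
4. Reconcile the remaining Possible bullets, including the one on negative rechallenge, which also points away from the drug.

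Align the CRF Completion Guidelines. Query causality for events already classified, serious ones first, before the lock of the part concerned. The parts lock separately (Protocol 7.9; Part A SAP 3.5). If Part A is already locked, keep the original calls in the main tables and show the re-confirmed calls as a sensitivity tabulation. The rules that use the relatedness call need no change.

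The cost is a wording amendment and a one-off query in about 20 patients. Re-asking causality in an open-label trial carries some hindsight risk; showing the original calls alongside makes any shift visible.
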